2.1. Primary Objective

The primary objective is to evaluate the effectiveness (measured by study retention rate) of ESL administered once daily (QD) as the first adjunctive therapy to levetiracetam (LEV) or lamotrigine (LTG) or as later adjunctive therapy in subjects with POS over a 24-week maintenance period in a real-world clinical setting.

2.2. Secondary Objectives

The secondary objectives are

- To evaluate the efficacy of ESL QD as a first or later adjunctive therapy based on the number of seizures reported over a 24-week maintenance period.
- To evaluate the safety and tolerability of ESL QD as a first or later adjunctive therapy.
- To evaluate the effect of treatment with ESL QD on the quality of life (QOL), behavior, and mood.

2.3. Exploratory Objectives

The exploratory objectives are

- To evaluate the accuracy of an investigational wearable watch device from Empatica in recording seizure counts.
- To evaluate the performance of an investigational electronic seizure diary in the form of a smartphone application (Empatica MATE).

2.4. Study Endpoints

2.4.1. Primary Endpoint

The primary endpoint is the proportion of subjects completing 24 weeks adjunctive therapy during Maintenance Phase (Visit 9).

2.4.2. Secondary Efficacy Endpoints

- Seizure data via the paper diary will be used to calculate the following seizure related endpoints:
 - Standard Seizure Frequency (SSF) during the first 12 weeks, the last 12 weeks, and the 24 weeks of the Maintenance Phase.
 - 50% and 75% responder rate (calculated as 50% and 75% reduction in SSF from baseline) as evaluated during the first 12 weeks, the last 12 weeks, and the 24 weeks of the Maintenance Phase.
 - Relative reduction (%) in SSF from baseline during the first 12 weeks, the last 12 weeks, and the 24 weeks of the Maintenance Phase.
 - Proportion of seizure-free subjects during the first 12 weeks, the last 12 weeks, and the 24 weeks of the Maintenance Phase.
- Time on ESL

2.4.3. Other Efficacy Endpoints

- Changes from baseline in the Neurological Disorders Depression Inventory for Epilepsy (NDDI-E)-6-item questionnaire.
- Changes from baseline in the Profile of Mood States Short-form (POMS-SF).
- Changes from baseline in the agitation/behavioral measurements as evaluated by the Modified Overt Aggression Scale (MOAS).
- Changes from baseline in Quality of Life in Epilepsy-Patient-Weighted (QOLIE-31-P) scores.
- Change from baseline in EuroQol Five Dimensions Questionnaire (EQ-5D) scores.
- Clinical Global Impression of Improvement (CGI-I) scores at each evaluation time point.
- Patient's Global Impression of Change (PGI-C) scores at each evaluation time point

2.4.4. Safety Endpoints

- Number and percentage of subjects with AEs.
- Number and percentage of subjects with serious adverse events (SAEs).
- Number and percentage of subjects with AEs leading to discontinuation.
- Electronic Columbia-Suicide Severity Rating Scale (eC-SSRS): Proportion (%) of events in each classification class (as completed by the subject).
- Changes from baseline in clinical laboratory parameters, including thyroid panel.
- Changes from baseline in vital signs parameters.
- Score of AED-specific AEs (by the Liverpool Adverse Event Profile [LAEP]).

2.4.5. **Exploratory Endpoints**

- Seizure data recorded by an investigational wearable watch device from Empatica.
- Seizure data recorded by an investigational electronic seizure diary from Empatica MATE application.

3. Study Design

3.1. General Description

This is a 31-week, multicenter, 2-arm, prospective, open-label, non-randomized, Phase 4 study of ESL as adjunctive therapy in adult subjects with a diagnosis of epilepsy with POS. Two groups of ESL-naïve subjects will be evaluated. The groups are defined as follows:

Arm 1 (ESL as first add-on): This group will include subjects who have been maintained on a regimen consisting of a stable dose of LEV or LTG for at least 1 month (28 days) prior to screening and who have not used any adjunctive treatment.

Arm 2 (ESL as later add-on): This group will include subjects who have been maintained on a regimen consisting of a stable dose of 1 - 2 anti-epileptic drugs (AEDs) (excluding oxcarbazepine [OXC]) for at least 1 month (28 days) prior to screening and who have used adjunctive treatment in the past.

The Arm 1 subjects will allow an assessment of the efficacy and safety of ESL in subjects who are early in the course of their disease and being treated with one of the most common first line AEDs. The subjects in Arm 2 are similar to the subject population in the Phase 3 adjunctive studies, treatment-resistant subjects who are later in the course of their disease. The inclusion of these subjects in the present study will provide an assessment of the efficacy and safety of ESL as a later adjunctive therapy in a real world clinical setting. In addition, this study will provide data from both Arm 1 and Arm 2 for several behavioral, mood-related, and QOL-related assessments that were not evaluated in the Phase 3 program.

Approximately 100 subjects will be enrolled (approximately 50 subjects in Arm 1 and 50 subjects in Arm 2).

The study will consist of a Screening Phase of 1 to 2 weeks, followed by a 2-week Titration Phase, a 24-week Maintenance Phase, and a Safety Follow-up/Taper Phase of 4 weeks. The last visit in the Maintenance Phase (Visit 9) is considered the End of Study (EOS) visit.

The screening visit should take place 7 - 10 days prior to the titration visit and may be extended to 7 - 17 days if required with consent of medical monitor. Subjects of Asian ancestry who require HLA-B*1502 testing (eg do not have prior test results) may have the screening visit 7 - 17 days prior to the titration visit.

Subjects who withdraw prior to the EOS visit should have an Early Discontinuation Visit (EDV) within 72 hours.

3.2. IXRS and Dispensing of Study Drugs

An Interactive Web/Voice Response System (IXRS) will be used to register the Screening Visit (Visit 1) and assignment of the Subject Screening number. If the Subject is enrolled in the study the Screening number becomes the Subject number. The IXRS will also be utilized to register the Titration Visit (Visit 2), Maintenance Phase Visits (Visit 3 – Visit 9) and EDV. Study drug will be dispensed based on assignment by the IXRS at Visits 2 – Visit 8. At Visit 9 and EDV the IXRS will give an option to dispense an additional bottle of study drug if needed for taper. Please ensure to dispense the correct lot number(s) assigned to each Subject. In addition, the IXRS will be utilized to register Screen Failure and Acknowledgment of study drug receipt at site.

3.3. Determination of Sample Size

Sample size is determined outside of statistical consideration. Approximately 100 subjects will be enrolled, almost evenly split between Arm 1 (first add-on) and Arm 2 (later add-on). Assuming the completion rates at 24 weeks of the Maintenance Phase are 60% and 50% for Arm 1 and Arm 2 respectively, the width of 95% CI for completion rate will be approximately 14% based on normal approximation method.

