15. STATISTICS

15.1. Sample Size

Sample size is calculated based on the precision (a half width of the 95% confidence interval [CI]) for the estimate of the completion rate as assumed as below and is used the Normal approximation to the Binomial distribution.

Arm 1 (first add-on): Assuming a completion rate of 60% at 24 weeks of the Maintenance Phase for Arm 1, to show the lower limit of the 95% CI in the rate to be 50% (50%, 70%), the sample size is estimated at approximately 93 subjects.

Arm 2 (later add-on): Assuming the completion rate of 50% at 24 weeks of the Maintenance Phase for Arm 2, to show the lower limit of the 95% CI in the rate to be 40% (40%, 60%), the sample size is estimated at approximately 97 subjects.

Total estimated subject enrollment is approximately 190 subjects.

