15.1.2. Primary Analysis of Primary Outcome Variable

The primary analysis will be performed for the safety population.

The number and proportion (%) of subjects completing the 24 weeks of the Maintenance Phase will be provided along with a 95% confidence interval using the exact method.

It will be also summarized by age group, race group, gender, baseline AEDs and number of baseline AEDs.

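### SAP 3.3 gives the half-width of the primary 95% CI (about 14 points) as its width; at 50 per arm the interval is about 27 to 29 points wide and misses the protocol's precision targets

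*SAP*

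**What the plan says.** SAP section 3.1 gives the size: "Approximately 100 subjects will be enrolled (approximately 50 subjects in Arm 1 and 50 subjects in Arm 2". Section 3.3 opens with "Sample size is determined outside of statistical consideration". It then sets the assumptions, "Assuming the completion rates at 24 weeks of the Maintenance Phase are 60% and 50% for Arm 1 and Arm 2 respectively", and concludes that "the width of 95% CI for completion rate will be approximately 14% based on normal approximation method". For the primary analysis, SAP section 15.1.2 says that the number and proportion completing "will be provided along with a 95% confidence interval using the exact method", in the safety population.

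The protocol plans differently. Section 15.1 says "Sample size is calculated based on the precision (a half width of the 95% confidence interval [CI", with the normal approximation. For Arm 1, at an assumed 60%, the aim is "to show the lower limit of the 95% CI in the rate to be 50% (50%, 70%), the sample size is estimated at approximately 93". For Arm 2, at an assumed 50%, the interval is 40% to 60% and the size 97. The total is about 190.

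SAP section 3.4.1 says only that four amendments have been incorporated. Section 3.4.2 lists only the dropped calculations of doses taken and average daily dose.

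**The concern.** The width of a confidence interval is the distance from its lower to its upper limit. With 50 subjects and a proportion near one half, that distance cannot be as small as 14 points. The protocol's intervals, from almost twice as many subjects, are 20 points wide. Read beside them, a 14% width suggests that the smaller study is the more precise one, when it is clearly less precise.

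The study tests no hypothesis and does not compare the arms. Its primary result is one completion rate with a 95% CI in each arm, and section 3.3 is the only place where the SAP says how precise that result will be. A reader who takes it at face value expects about plus or minus 7 points and will get about plus or minus 14. The lower limits that the protocol was sized to reach would also be lost without either document saying so.

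**Working it through.** **Inputs.** Rates of 60% (Arm 1) and 50% (Arm 2), from SAP 3.3 and Protocol 15.1. Size of 50 per arm, from SAP 3.1; 93 and 97, from Protocol 15.1. Two-sided 95% level, z = 1.96. Normal approximation for planning (both documents); exact method for the primary analysis (SAP 15.1.2). Non-completers stay in the safety-population denominator, so no allowance for dropout is needed.

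**Formulas.** Half-width h = z × √(p(1 − p)/n). Full width = 2h. Size for a given half-width: n = z² × p(1 − p)/h².

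**Step 1: the protocol's sizes.** With h = 0.10:
- Arm 1: 3.8416 × 0.24/0.01 = 92.2, rounded up to 93.
- Arm 2: 3.8416 × 0.25/0.01 = 96.04, rounded up to 97.

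Both reproduce, and both are sized on the half-width.

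**Step 2: the SAP's 14%.** At n = 50:
- Arm 1: h = 1.96 × √(0.24/50) = 0.1358, so the full width is 0.272 and the interval 46.4% to 73.6%.
- Arm 2: h = 1.96 × √(0.25/50) = 0.1386, so the full width is 0.277 and the interval 36.1% to 63.9%.

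The 14% reproduces as the half-width and not as the width.

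**Step 3: other readings of 14% as a full width** (points).

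| Reading | Arm 1 | Arm 2 |
|---|---|---|
| Normal, n = 50 | 27.2 | 27.7 |
| Normal, n = 100 (both arms taken as one) | 19.2 | 19.6 |
| Normal, n = 50, z = 1.645 | 22.8 | 23.3 |
| Wilson, n = 50 | 26.2 | 26.7 |
| Exact (Clopper-Pearson), n = 50 | 28.4 | 28.9 |

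None is near 14. A continuity correction only widens the interval.

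**Step 4: size needed for a true width of 14 points** (h = 0.07). Arm 1: 3.8416 × 0.24/0.0049 = 188.2, rounded up to 189. Arm 2: 3.8416 × 0.25/0.0049 = 196.

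**Step 5: lower limits at 50 per arm against the protocol's targets.**

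| | Target | Normal | Shortfall | Exact | Shortfall |
|---|---|---|---|---|---|
| Arm 1 (30/50) | 50% | 46.4% | 3.6 | 45.2% | 4.8 |
| Arm 2 (25/50) | 40% | 36.1% | 3.9 | 35.5% | 4.5 |

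The exact upper limits are 73.6% and 64.5%.

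**The case against.** Nobody disputes the arithmetic. The case on the other side concerns weight.

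- **The SAP does not size the study on 14%.** It says openly that the size was set on other grounds, and it nowhere undertakes to reach lower limits of 50% and 40%. This stands. The charge is that precision is misdescribed and the protocol's targets lapse unannounced, not that the SAP breaks a promise of its own.
- **This is a wrong label on a right number.** The primary interval will be computed from the data, and no decision rule depends on 14%. That also stands, and it limits the harm to the planning statement. But loose usage is a weak excuse when the protocol itself names the half-width as its measure of precision.
- **The protocol version is uncertain.** The SAP's introduction says it rests on version 3.02 of 04 October 2018. The title page of the supplied protocol is not available, so its version cannot be confirmed. If version 3.02 already plans about 100 subjects, there is no conflict between the governing documents. This limits the reconciliation point only; the width error lies wholly within SAP section 3.3.
- **Methods should not be mixed.** The protocol's targets were set by normal approximation, so the like-for-like shortfalls are 3.6 and 3.9 points. By the exact method even the protocol's sizes sit at the boundary: 56/93 has a lower limit of 49.5% and 48/97 one of 39.2%. This is fair, and both methods are shown above for that reason. Planning by approximation and analysing exactly is not in itself an error; at this size it adds only 1.2 points of width.

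**Conclusion.** The concern holds. SAP section 3.3 calls a half-width a width and so states the precision of the primary estimate as twice what it is: about 14 points stated, against 27.2 and 27.7 by its own method and 28.4 and 28.9 by the planned exact method. At 50 per arm the protocol's lower limits of 50% and 40% are missed by 3.6 and 3.9 points (normal) or 4.8 and 4.5 points (exact). The supplied protocol and the SAP differ by about 90 subjects, and SAP section 3.4 does not say so.

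The figures assume exactly 50 per arm and observed rates equal to the assumed 60% and 50%. With 45 to 55 per arm the normal-approximation widths run from 28.6 down to 25.9 points (Arm 1) and from 29.2 down to 26.4 (Arm 2), so the conclusion does not turn on the exact split. The statement that the two documents disagree on enrolment applies to the protocol as supplied.

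**What to change.** 1. In SAP section 3.3, replace the width statement with: the half-width of the 95% CI is approximately 14 percentage points by normal approximation; with the exact method the interval would be about 45% to 74% in Arm 1 (30/50) and 36% to 64% in Arm 2 (25/50).
2. Add there that the protocol's lower limits of 50% and 40% no longer apply at this size.
3. Record the reduction from about 190 to about 100 subjects, with its reason, in SAP section 3.4.1.
4. Confirm which protocol version governs. If it still plans 93 and 97, bring its section 15.1 and the other statements of 190 subjects (synopsis and section 7.1) into line with the SAP.

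The cost is a few sentences in the SAP and a reconciling change in the protocol if the version check calls for it. The stated precision becomes less favourable. No subject is added, and the primary analysis stays as it is.

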3.4. Changes in the Conduct of the Study or Planned Analyses

3.4.1. Change in the Conduct of the Study

Four amendments have been incorporated into protocol since final protocol.

3.4.2. Changes from Analyses Planned in the Protocol

Since the study drug accountability data was not collected in the data source, the number of dose taken and average daily dose will not be calculated.

3.5. Schedule of Assessments

Study Period	Screening	Titration ^a	24-Week Maintenance Phase ^a										EDV ^a	Safety Follow-up
Visit	V1	V2	V3	V4	TC1	V5	V6	TC2	V7	V8	V9 (EOS)			V10 or TC3
Week	-1 to -20 Wks	WK 1 Day 1	WK 3	WK 7	WK 9	WK 11	WK 15	WK 17	WK 19	WK 23	WK 27			WK 31
Windows (days)	(+3)	-	±3	±3	±3	±3	±3	±3	±3	±3	±3			±7
Procedures														
Informed Consent Form	X	-	-	-	-	-	-	-	-	-	-	-	-	-
Genetic Consent for HLA-B*1502 Characterization: Subjects of Asian Ancestry only ^{b,o}	X	-	-	-	-	-	-	-	-	-	-	-	-	-
Genetic Consent for HLA genotyping (optional) ^c	X	-	-	-	-	-	-	-	-	-	-	-	-	-
Review of Inclusion/ Exclusion Criteria ^a	X	X	-	-	-	-	-	-	-	-	-	-	-	

Study Period	Screening	Titration ^a	24-Week Maintenance Phase ^a										EDV ^a	Safety Follow-up
Visit	V1	V2	V3	V4	TC1	V5	V6	TC2	V7	V8	V9 (EOS)		V10 or TC3	
Week	-1 to -20 Wks	WK 1 Day 1	WK 3	WK 7	WK 9	WK 11	WK 15	WK 17	WK 19	WK 23	WK 27		WK 31	
Windows (days)	(+3)	-	±3	±3	±3	±3	±3	±3	±3	±3	±3		±7	
Procedures														
Demographics	X	-	-	-	-	-	-	-	-	-	-	-	-	
Medical and Neurologic History	X	-	-	-	-	-	-	-	-	-	-	-	-	
Complete DISCOVER form	X	-	-	-	-	-	-	-	-	-	-	-	-	
Administer HEP and Collect Seizure History Data ^d	X	-	-	-	-	-	-	-	-	-	-	-	-	
Prior/Concomitant Medications ^e	X	X	X	X	-	X	X	-	X	X	X	X	X	
Physical/Neurologic Examination	X	-	X	X	-	X	X	-	-	X	X	X	-	
Vital Signs	X	X	X	X	-	X	X	-	X	X	X	X	-	
Body Weight	X	X	X	X	-	X	X	-	X	X	X	X	-	
Height	X	-	-	-	-	-	-	-	-	-	-	-	-	
12-lead ECG	X	-	-	-	-	-	-	-	-	-	X	X	-	
Clinical Laboratory Tests ^f	X										X	X		

Study Period	Screening	Titration ^a	24-Week Maintenance Phase ^a										EDV ^a	Safety Follow-up
			V3	V4	TC1	V5	V6	TC2	V7	V8	V9 (EOS)			
Visit	V1	V2												V10 or TC3
Week	-1 to -20 Wks	WK 1 Day 1	WK 3	WK 7	WK 9	WK 11	WK 15	WK 17	WK 19	WK 23	WK 27			WK 31
Windows (days)	(+3)	-	±3	±3	±3	±3	±3	±3	±3	±3	±3			±7
Thyroid panel (free T3, T4, and TSH)	X	-	-	-	-	-	-	-	-	-	-	X	X	-
Blood Sample for HLA-B*1502 testing: Subjects of Asian ancestry only ^g	X	-	-	-	-	-	-	-	-	-	-			-
Genetic Saliva Sample and Questionnaire (optional) ^h	-	-	-	X	-	-	-	-	-	-	-			-
Serum β-hCG ⁱ	X	-	-	-	-	-	-	-	-	-	-	X	X	-
Urine Pregnancy Test ⁱ	-	X	X	X	-	X	X	-	X	X				
Urine Drug Screen	X													
Liverpool Adverse Event Profile ^j	-	X	X	X	-	X	X	-	X	X	X	X	-	
Adverse Events	-	X	X	X	X	X	X	X	X	X	X	X	X	X

Study Period	Screening	Titration ^a	24-Week Maintenance Phase ^a										EDV ^a	Safety Follow-up
			V3	V4	TC1	V5	V6	TC2	V7	V8	V9 (EOS)			
Visit	V1	V2	WK 3	WK 7	WK 9	WK 11	WK 15	WK 17	WK 19	WK 23	WK 27		V10 or TC3	
Week	-1 to -20 WKS	WK 1 Day 1											WK 31	
Windows (days)	(+3)	-	±3	±3	±3	±3	±3	±3	±3	±3	±3		±7	
Procedures														
Pre-treatment Adverse Events	X	-	-	-	-	-	-	-	-	-	-		-	-
Dispense Study Drug	-	X	X	X	-	X	X	-	X	X	X ^k	X ^p	-	
Collect Study Drug	-	-	X	X	-	X	X	-	X	X	X	X	-	-
Record Any ESL Dose Change Since Last Visit	-	-	X	X	X	X	X	X	X	X	X	-	-	
Record Any AED Dose Change Since Last Visit	-	-	X	X	X	X	X	X	X	X	X	X	-	-
Distribute Empatica Watch ^l	X	-	-	-	-	-	-	-	-	-	-	-	-	-

Study Period	Screening	Titration ^a	24-Week Maintenance Phase ^a										EDV ^a	Safety Follow-up
Visit	V1	V2	V3	V4	TC1	V5	V6	TC2	V7	V8	V9 (EOS)		V10 or TC3	
Week	-1 to -20 Wks	WK 1 Day 1	WK 3	WK 7	WK 9	WK 11	WK 15	WK 17	WK 19	WK 23	WK 27		WK 31	
Distribute Paper Seizure Diary ^m	X	X	X	X	-	X	X	-	X	X	X	X	-	
Collect Paper Seizure Diary	-	X	X	X	-	X	X	-	X	X	X	X	-	
Review Seizure Diaries		X	X	X	-	X	X	-	X	X	X	X	X ^q	
EQ-5D	-	X	-	-	-	X	-	-	-	-	X	X	-	
CGI-I			X	-	-	X	-	-	-	-	X	X	-	
PGI-C			X	-	-	X	-	-	-	-	X	X	-	
QOLIE-31-P	-	X	-	-	-	X	-	-	-	-	X	X	-	
POMS-SF	-	X	-	-	-	X	-	-	-	-	X	X	-	
NDDI-E	-	X	-	-	-	X	-	-	-	-	X	X	-	
MOAS	-	X	-	-	-	X	-	-	-	-	X	X	-	
eC-SSRS ⁿ	X	X	X	X	-	X	X	-	X	X	X	X	-	
Return of watch and data collection device	-	-	-	-	-	-	-	-	-	-	X	X	-	

Abbreviations: AED = Antiepileptic drug; β -hCG = Beta-human chorionic gonadotropin; CGI-I – Clinical Global Impression of Improvement; CRF = case report form; eC-SSRS = electronic Columbia-Suicide Severity Rating Scale; DISCOVER = Diagnostic Interview for Seizure Classification Outside of Video EEG Recording; ECG = Electrocardiogram; EDV = Early Discontinuation Visit; EOS = End of Study; EQ-5D = EuroQol Five Dimensions Questionnaire; ESL = Eslicarbazepine acetate; HEP = pre-Human Epilepsy Project; HLA = Human Leukocyte Antigen; MOAS = Modified Overt Aggression Scale; NDDI-E = Neurological Disorders Depression Inventory for Epilepsy; PGI-C = Patient's Global Impression of Change; POMS-SF = Profile of Mood States Short-form; QOLIE-31-P = Quality of Life in Epilepsy-Patient-Weighted (31-item); T3 = Triiodothyronine; T4 = Thyroxine; TC = telephone call; TSH = Thyroid Stimulating Hormone; US = United States; WK = Week

a Eligible subjects will begin the 2-week Titration Phase on Day 1 (Week 1), during which they will initiate treatment with ESL at 400 mg/day and remain on that dose for 1 week (Days 1 – 7). Subjects will titrate to ESL 800 mg/day the beginning of week 2 (Day 8) and will remain on that dose for 1 week up to the beginning of the maintenance phase. Subjects will maintain a minimum dose of 800 mg/day for the Maintenance Phase; however, during the Maintenance Phase, subjects may titrate in weekly increments of 400 mg/day as medically indicated at the discretion of the Investigator up to a maximum dose of 1200 mg/day (Canadian Sites) or 1600 mg/day (US sites), (based on maximum local labelled dose). Additional details are provided in Section 10.1.1. Subjects who withdraw prior to the (end of study) EOS visit should have an early discontinuation visit (EDV) within 72 hours.

b Subjects of Asian ancestry (or subjects for whom the absence of Asian ancestry cannot be confirmed) who cannot provide documentation stating that they are not carriers of HLA-B*1502 must give written informed consent for genotyping. Asian ancestry will be based on subject self-report.

c This consent for genetic saliva sample and associated questionnaire is optional.

d Record seizure history (the number and types of seizures that occurred over the longest available period up to 3 months prior to screening).

e Record all prior and concomitant medications, including over the counter medications, taken within the previous 60 days.

f Includes clinical chemistry, hematology and urinalysis. Estimated creatinine clearance using Cockcroft-Gault equation at Screening only.

g Required for subjects of Asian ancestry (or subjects for whom the absence of Asian ancestry cannot be confirmed) and who do not have documentation to show that they are not carriers of HLA-B*1502.

h Subjects who provided optional separate informed consent/assent only.

i A serum pregnancy test will be given to all female subjects of childbearing potential at screening. An on-site urine pregnancy test will be given to all female subjects of childbearing potential at Visits 1-8. Any positive urine pregnancy test will be followed up with a serum test for confirmation of pregnancy. A serum pregnancy test will be given to all females subjects of childbearing potential at Visit 9 (EOS) or at the EDV.

j The Liverpool Adverse Event Profile collects information on AEs associated with AEDs.

k Subjects who elect to continue on commercially available drug will not be dispensed additional ESL at this visit. Subjects who elect to discontinue ESL will be provided sufficient ESL to accommodate the appropriate taper regimen.

l Subjects will be provided with the Empatica watch and instructed in the use of the watch.

m Subjects will be provided a standardized paper daily seizure diary and an electronic daily seizure diary and instructed in the use of the diaries. Diaries are to be completed daily whether a seizure occurs or not.

n The “Baseline/Screening” (lifetime) version should be administered at the screening visit and the “Since Last Visit” version at all other time points.

o The screening visit should take place 7 - 10 days prior to the titration visit, and may be extended to 7 – 17 days if required with consent of medical monitor. Subjects of Asian ancestry who require HLA-B*1502 testing (eg, do not have prior test results) may have the screening visit 7 - 17 days prior to the titration visit.

p Subjects who discontinue prior to the EOS visit will be provided sufficient ESL to accommodate the appropriate taper regimen.

q At the Safety Follow-Up visit, the standardized paper daily seizure diary will not be collected; however it will be reviewed as part of the subject’s safety assessments.

4. Planned Analyses

The following analyses will be performed for this study:

- Final Analysis

